B	August 14, 2019	AL	Contact Information, Protocol Synopsis, Section 1.2, Section 4	The list of Coordinating Principal Investigators was reduced from 7 to 2 The planned number of subjects was increased from 500 to 1000 Additional information was added to the study rationale Minor additional changes throughout	Per Investigator feedback
C	June 16, 2020	92120219, Rev/Ver C	Protocol Synopsis, Section 1.2 Study Rationale, Table 5.3-1, Section 14.1 Potential Risks and Benefits, Section 16.4 Investigator Reporting Requirements	Protocol Synopsis updated to change maximum number of sites from 20 to 40, and Altered Pancreaticobiliary Anatomy exclusion criterion removed Section 1.2 updated to reflect the commercial availability of EXALT Table 5.3-1 updated to remove Altered Pancreaticobiliary Anatomy exclusion criterion Section 14.1 updated to refer to product DFU Section 16.4 updated to reflect post-market reporting timelines Various minor terminology updates throughout	Per Investigator feedback the Altered Pancreaticobiliary Anatomy exclusion criterion was removed. Because Exalt is commercially available it can be used in patients with altered pancreaticobiliary anatomy outside of this study, and this is not listed as a contraindication in the DFU. The intent of this study is to evaluate the performance of Exalt Model D in ERCPs and other duodenoscopy-based procedures. "Altered pancreaticobiliary anatomy" is not a contraindication for the use of Exalt in the approved DFU. This exclusion criterion was originally included due to questions of how well Exalt would be able to navigate tortuous GI anatomy based on insertion shaft stiffness, however

Revision Version	Protocol Date	Template Number and Version	Protocol Section Modified	Summary of Changes	Justification for Modification
					
these concerns have been resolved by the clinical experience to date.
 
Update to Clinical Study Protocol Template (Post-Market) 92120219 after FDA 510(k) clearance of the study device

D	January 14, 2022	92120219, Rev/Ver G	Cover Page; Section 3 Study Objectives and Endpoints; Section 9.1 Data Collection, Processing, and Review; Section 16 Safety Reporting	Cover page updated to include NCT Identification Number Section 3 updated to include Justification for Endpoints Section 9.1 updated to include additional paragraph to specify the changes in clinical database access after data is Hard Locked or Entry Locked Update to section 16.2 to change the Ref from MEDDEV to MDCG, and changes to the safety definitions to align with the updated guidance Update to section 16.3 to change the Ref from MEDDEV to MDCG, and changes to the AE definitions to align with the updated guidance Changes made to table 16.4-1 to align with the update guidance Various minor terminology updates throughout	Update to incorporate the changes made to the protocol template 92120219 from Ver. C to Ver. G.

Protocol Synopsis

Global Prospective Case Series using a Single-Use Duodenoscope Exalt DScope 02 E7156	
Study Objective(s)	Confirm procedural performance of the Exalt™ Model D Single-Use Duodenoscope in Endoscopic Retrograde Cholangio-Pancreatography (ERCP) and other duodenoscope-based procedures
Indication(s) for Use	Single-Use Duodenoscope The device is intended for use with the Controller, for endoscopy and endoscopic surgery within the duodenum. Video Imaging System Controller The device is intended for use with a Boston Scientific endoscope for endoscopic diagnosis, treatment, and video observation.
Study Device and sizes, if applicable	Exalt™ Model D Single-Use Duodenoscope Exalt™ Controller
Study Design	Prospective case series of per standard of care ERCP procedures or other duodenoscope-based procedures
Planned Number of Subjects	Up to 1000 subjects
Planned Number of Investigational Sites	Up to 40 sites
Primary Endpoint	Ability to complete the ERCP or other duodenoscope-based procedure for the intended indication(s)
Secondary Endpoints	1. Document endoscopist rating of the Exalt single-use duodenoscope compared to marketed reusable duodenoscopes as it pertains to various design and performance related attributes

Global Prospective Case Series using a Single-Use Duodenoscope Exalt DScope 02 E7156	
	
 2. Incidence of crossover from Exalt single-use duodenoscope to reusable duodenoscope 3. Evaluation of serious adverse events (SAEs) related to the device and/or the procedure through 30 days after the ERCP or duodenoscope-based procedure
Follow-up Schedule	
 • Screening/Baseline • Index Procedure • 72-hr Follow-Up Visit • 30 day Follow-Up Visit
Participant Duration	The study duration for each subject is expected to be approximately 1 month
Inclusion Criteria	
 1. 18 years or older 2. Willing and able to comply with the study procedures and provide written informed consent to participate in the study 3. Scheduled for a clinically indicated ERCP or other duodenoscope-based procedure
Exclusion Criteria	
 1. Potentially vulnerable subjects, including, but not limited to pregnant women 2. Subjects for whom endoscopic techniques are contraindicated 3. Subjects who are currently enrolled in another investigational study that would directly interfere with the current study, without prior written approval from the sponsor 4. Investigator discretion
Statistical Methods	
Statistical Hypothesis	A statistical hypothesis is not required for this study as it is a case series of per standard of practice ERCP or other duodenoscope-based procedures

Table of Contents

TITLE PAGE	1
PROTOCOL SYNOPSIS	6
TABLE OF CONTENTS	8
Table of Tables.....	11
1. INTRODUCTION.....	12
1.1. Background.....	12
1.2. Study Rationale	12
2. STUDY DEVICE DESCRIPTION.....	13
3. STUDY OBJECTIVES AND ENDPOINTS	14
4. STUDY DESIGN	15
4.1. Justification for the Study Design.....	15
5. SUBJECT SELECTION.....	15
5.1. Study Population and Eligibility.....	15
5.2. Inclusion Criteria	15
5.3. Exclusion Criteria	15
6. SUBJECT ACCOUNTABILITY.....	16
6.1. Point of Enrollment.....	16
6.2. Withdrawal.....	16
6.3. Lost to Follow-Up.....	16
6.4. End-of-Study Definition.....	17
7. STUDY METHODS	17
7.1. Data Collection	17
7.2. Study Candidate Screening.....	17
7.2.1. Strategies for Recruitment and Retention.....	18
7.3. Informed Consent.....	18

- 7.4. **Baseline.....18**
- 7.5. **Index Procedure18**
- 7.6. **72 hour (-1 day, + 2 days) and 30 day (\pm 3 days) Assessments.....18**
- 7.7. **Study Completion.....18**
- 7.8. **Source Documents18**
- 8. **STATISTICAL CONSIDERATIONS19**
 - 8.1. **Statistical Hypothesis and sample size justification19**

1.1. Background

Flexible endoscopes are used globally for the diagnosis and treatment of diseases of the GI tract. These delicate instruments are used in Endoscopic Retrograde Cholangiopancreatography (ERCP) procedures, which are performed with side viewing endoscopes (duodenoscopes) that to date are all reusable devices.¹ Given their reusability, these instruments must be reprocessed through high level disinfection (HLD) in order to prevent the spread of nosocomial infections², although different levels of disinfection may be produced depending on disinfection method, device modification, and staff adherence to disinfection protocols.^{1,3-5}

In recent years there have been an increased number of nosocomial infection outbreaks traced to contaminated duodenoscopes used during ERCP procedures in many states throughout the US and Europe.^{3,6-8} Organisms involved in these recent outbreaks include Carbapenem-resistant Enterobacteriaceae (CRE), including *Escherichia coli*, and *Klebsiella pneumoniae*.⁶ Unfortunately, some of the cases linked to these outbreaks have proven to be fatal.⁸ Typically, infections discovered post-ERCP procedures vary between 2%-4%⁹, but it is unclear whether these infections are caused by contaminated duodenoscopes or the procedure.⁶

The gastrointestinal tract is a highly contaminated environment, and the intricate tip design and long, narrow working channels of modern duodenoscopes render them extremely difficult, if not impossible, to adequately clean.¹⁰ Even strict adherence to all HLD procedures results in a non-zero, although minimal, level of potentially infectious microbes.¹⁰ This remains a large problem, and neither manufacturers or regulatory bodies, such as the FDA, were providing guidance for this. While these cases reported in the hospitals listed above occurred in 2012, several other cases emerged globally, and months later the FDA stated that they were warning manufacturers, monitoring, and providing closer surveillance in an effort to prevent further infections associated with contaminated duodenoscopes.¹¹ The FDA mandated the three duodenoscope manufacturers in the US, Olympus, Pentax, and Fujifilm, conduct post-market surveillance studies to evaluate the rate of duodenoscope contamination with viable microorganisms after standard HLD in actual practice. While the studies assumed a <0.4% contamination rate, the study revealed 5.4% of duodenoscopes interrogated for these studies remained contaminated with high concern microorganisms including *E. coli* and *Pseudomonas aeruginosa*.¹²

1.2. Study Rationale

Conventional reusable duodenoscopes have been identified as the source of multiple cases of fatal and non-fatal nosocomial infections throughout the US and Europe, despite adherence to duodenoscope sterilization and reprocessing guidelines. In some cases, the infectious organisms were later identified as belonging to a family of bacteria that has a high level of resistance to conventional antibiotics, known as CRE. The Exalt™ Model D Single-Use

Duodenoscope is the first single-use disposable duodenoscope available on the open market, which does not need to be sterilized or reprocessed because they are only used for a single patient in one case before they are disposed of. The availability of this device may save patient lives by removing a potential source of infection and save the healthcare system money used to treat the infections and to reprocess the devices.

In April-May 2019, 60 patients were prospectively enrolled in a consecutive ERCP case series using the Exalt™ Model D Single-Use Duodenoscope. The primary endpoint of this study was the ability to complete the ERCP or other duodenoscope-based procedure for the intended indication(s). All 60 (100%) ERCPs were completed, 58 (97%) using the single-use duodenoscope only, and 2 (3%) with crossover to a reusable duodenoscope.

2. Study Device Description

The Exalt™ Model D Single-Use Duodenoscope is a sterile, single-use endoscope that facilitates access to the duodenum, delivery of accessories, and live video when connected to an Exalt™ Controller.

The Exalt™ Controller is an electronic device that:

- Receives video signals from a Boston Scientific single-use endoscope,
- Processes the video signals,
- Outputs video images to a video monitor, and
- Outputs electrical signal(s) that interface with external image capture systems.

The Controller also controls the light transmitted by the tip of the single-use endoscope to illuminate the area of interest within the anatomy. Buttons on the Controller's front panel enable the user to control the brightness level of the light.

To use the Controller, connect it to a video monitor with a video cable and then connect a Boston Scientific single-use endoscope to the Controller. The Controller provides direct visualization during an endoscopic procedure.

The Controller interfaces with external media capture equipment via the Controller's rear panel connectors. Image capture is initiated via a button on the Boston Scientific single-use endoscope. The Controller sends a signal to the video monitor notifying the user that an image capture has been initiated. Directions for use for the Exalt™ Model D Single-Use Duodenoscope and Exalt™ Controller will be supplied separately to the investigational site in a regulatory binder. Investigators will use the device in accordance with the supplied directions and their institutional standard of care.

3. Study Objectives and Endpoints

Table 3-1: Study Objectives and Endpoints

OBJECTIVES	ENDPOINTS	JUSTIFICATION FOR ENDPOINTS
Primary Endpoints		
To confirm procedural performance of the Exalt™ Model D Single-Use Duodenoscope in Endoscopic Retrograde Cholangio-Pancreatography (ERCP) and other duodenoscope-based procedures	The primary endpoint is the ability to complete the ERCP procedures for the intended indication(s).	Completion of ERCP and other duodenoscope based procedures is the standard measurement of the performance of a duodenoscope. This endpoint will indicate that these procedures can be achieved with the Exalt duodenoscope.
Secondary Endpoints		
To confirm procedural performance of the Exalt™ Model D Single-Use Duodenoscope in Endoscopic Retrograde Cholangio-Pancreatography (ERCP) and other duodenoscope-based procedures	The following will be recorded as secondary endpoints during index procedure through follow-up: 
 1. Document endoscopist rating of the Exalt single-use duodenoscope compared to marketed reusable duodenoscopes as it pertains to various design and performance related attributes. 2. Incidence of crossover from Exalt single-use duodenoscope to reusable duodenoscope. 3. Evaluation of serious adverse events (SAEs) related to the device and/or the procedure through 30 days after the ERCP or other duodenoscope based procedures 	
 1. Endoscopist rating of the study device provide a subjective evaluation of the device performance by intended users. 2. The ability to complete the index procedure with the Exalt duodenoscope is an important indicator of the performance of the device. 3. Serious adverse events are being collected at 30 days in order to detect any event with a late onset and to document the safety profile of the study device.

4. Study Design

This is a prospective, multi-center case series of standard of care ERCP procedures and other duodenoscope-based procedures with up to 1000 subjects. This study represents the post-market clinical development stage of the study device according to ISO 14155. The endoscopist will use the Exalt single-use duodenoscope in place of the reusable duodenoscope normally used in the endoscopy unit at their own discretion.

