A subject will be considered lost to follow-up if he/she fails to return for their scheduled follow-up visits and is unable to be contacted by the study site staff after at least three documented attempts, at which point an End of Study form should be completed. Before a participant is deemed lost to follow up, the investigator or designee will make every effort to regain contact with the participant (where possible, 3 telephone calls and, if necessary, a certified letter to the participant's last known mailing address or local equivalent methods).

These contact attempts should be documented in the participant's medical record or study file.

6.4. *End-of-Study Definition*

A clinical trial is considered completed when participants are no longer being examined or the last participant's last study visit has occurred.

Subjects will be followed through 30 days post index procedure. At study completion, an End of Study form will be completed. The end of study is defined as completion of the last visit or a reason for the last study visit not having been completed has been determined by the investigator or designee. If the last follow-up visit was not completed, the investigator will note the reason on the study completion form (e.g. subject withdrawn by investigator, subject withdrew consent, lost to follow-up, AE, death, etc.).

7. Study Methods

7.1. *Data Collection*

The data collection schedule is shown in Table 7-1.

Table 7-1: Data Collection Schedule					
Procedure/Assessment	Screening	Baseline	Index Procedure	Follow-up Visits	
				72-hour visit (-1, +2 Days) Office/ Telephone	Day 30 visit (± 3 Days) Office/ Telephone
Informed consent process, including informed consent signature date	X				
Demographics, Medical History		X			
Index Procedure			X		
Maneuvers			X		
Exalt Evaluation			X		
Device Event Assessment			X		
Adverse Event Assessment			X	X	X
End of Study					X

X=required

7.2. *Study Candidate Screening*

Subjects who are clinically indicated for an ERCP or other duodenoscope-based procedure and meet the listed eligibility criteria may be screened for trial enrollment. All patients who are considered for enrollment but not enrolled will be recorded.

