7.2.1. Strategies for Recruitment and Retention

All patients under the care of a study investigator during the enrollment period of a site will be considered for recruitment.

7.3. *Informed Consent*

Data collection and/or study procedure will not occur prior to the subject signing the ICF. Patients will be considered enrolled in the study once they sign the informed consent. Once a subject is considered enrolled in the study, baseline information may be obtained.

7.4. *Baseline*

Baseline information will include the following data points: age at time of consent, gender, and relevant medical history.

7.5. *Index Procedure*

During the index procedure, the endoscopist or designated member of study staff will record: start and stop times of procedure, scope information, whether certain types of medicine were administered, and any activities completed or attempted during the procedure, regardless of original intent. Any ensuing device events will be recorded and reported.

After the ERCP procedure has been completed, the endoscopist will rate their experience using the Exalt device during the index procedure.

7.6. *72 hour (-1 day, + 2 days) and 30 day (± 3 days) Assessments*

All enrolled subjects will be seen in person or evaluated via telephone to screen for any post-procedure adverse events, and to evaluate the resolution of any previously noted adverse events or sequelae, as applicable.

7.7. *Study Completion*

Subjects will be followed for 30 days (± 3 days) post index procedure. Subjects will continue to receive care from their doctor as they normally would. At study completion, an End of Study form will be completed, indicating whether the subject completed the study. If the last follow-up visit was not completed, the reason will be noted on the study completion form (e.g. subject withdrawn by investigator, subject withdrew consent, lost to follow-up, AE, death, etc.).

7.8. *Source Documents*

It is preferable that original source documents are maintained, when available. In lieu of original source documents, certified copies are required to be maintained. A certified copy is a copy (irrespective of the type of media used) of the original record that has been verified

(i.e., by a dated signature or by generation through a validated process) to have the same information, including data that describe the context, content, and structure, as the original.

8. Statistical Considerations

8.1. *Statistical Hypothesis and sample size justification*

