Recent literature has identified an outbreak with carbapenem-resistant Enterobacteriaceae (CRE).³⁻⁸ That endoscopic transmission of infection can be prevented by strict adherence to disinfection protocols has been challenged with no clearly identified protocol to reduce this risk.¹³ Use of a Single-Use Duodenoscope would alleviate the need for high level disinfection of the standard Duodenoscope, thereby reducing the risk of infection transmission between patients.

15.5. *Risk to Benefit Rationale*

Based on collected reports in literature to-date, the risk-to-benefit ratio is within reason for foreseeable risks. However, literature reports do not always capture all side effects. Observation and follow-up of patients is required as outlined in the protocol.

16. Safety Reporting

16.1. *Reportable Events by Investigational Site to Boston Scientific*

It is the responsibility of the investigator to assess and report to BSC any event which occurs in any of following categories:

- All Non-Serious Adverse Events
- All Serious Adverse Events
- All Study Device Deficiencies

- Unanticipated Adverse Device Effects/Unanticipated Serious Adverse Device Effects
- New findings/updates in relation to already reported events

When possible, the medical diagnosis should be reported as the Event Term instead of individual symptoms.

If it is unclear whether or not an event fits one of the above categories, or if the event cannot be isolated from the device or procedure, it should be submitted as an adverse event and/or device deficiency.

Any reportable event, experienced by the study subject after informed consent and once considered enrolled in the study (as defined in study subject classification section), whether during or subsequent to the procedure, must be recorded in the eCRF.

Underlying diseases and chronic conditions are not reported as AEs unless there is an increase in severity or frequency during the course of the investigation. Death should not be recorded as an AE, but should only be reflected as an outcome of one (1) specific SAE (see Table 16-1 for AE definitions).

Refer to Section 15 for the known risks associated with the study device(s).

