16.4. Investigator Reporting Requirements

The communication requirements for reporting to BSC are as shown in Table 16-3.

Table 16-3: Investigator Reporting Requirements

Event Classification	Communication Method	Communication Timeline pre-market studies (21 CFR Part 812, MDCG 2020-10/1)	Communication Timeline post-market studies (EU MDR 2017/745, MDCG 2020-10/1 MEDDEV 2.12/1: GUIDELINES ON A MEDICAL DEVICE VIGILANCE SYSTEM)
Unanticipated Adverse Device Effect / Unanticipated Serious Adverse Device Effect	Complete AE eCRF page with all available new and updated information.	
 • Within 1 business day of first becoming aware of the event. • Terminating at the end of the study 	
 • Within 1 business day of first becoming aware of the event • Terminating at the end of the study
	Provide all relevant source documentation (de-identified/pseudonymized) for reported event.	
 • Upon request of sponsor. 	
 • At request of sponsor.
Serious Adverse Event	Complete AE eCRF page with all available new and updated information.	
 • Within 3 calendar days of first becoming aware of the event or as per local/regional regulations. • Reporting required through the end of the study 	
 • Within 10 calendar days of first becoming aware of the event or as per local/regional regulations. • Reporting required through the end of the study
	Provide all relevant source documentation (de-identified/pseudonymized) for reported event.	
 • Upon request of sponsor 	
 • When documentation is available. • Upon request of sponsor
Serious Adverse Device Effects	Complete AE eCRF page with all available new and updated information.	
 • Within 3 calendar days of first becoming aware of the event or as per local/regional regulations. 	
 • Within 3 calendar days of first becoming aware of the event or as per local/regional regulations.

Table 16-3: Investigator Reporting Requirements

Event Classification	Communication Method	Communication Timeline pre-market studies (21 CFR Part 812, MDCG 2020-10/1)	Communication Timeline post-market studies (EU MDR 2017/745, MDCG 2020-10/1 MEDDEV 2.12/1: GUIDELINES ON A MEDICAL DEVICE VIGILANCE SYSTEM)

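### Does a final contact allowed from day 27 undermine an SAE endpoint that runs through 30 days?

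*Combined protocol and SAP*

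**What the plan says.** The horizon is stated without a window in two places. Table 3-1 gives the third secondary endpoint as "Evaluation of serious adverse events (SAEs) related to the device and/or the procedure through 30 days after the ERCP or other duodenoscope based procedures", and Section 6.4 says "Subjects will be followed through 30 days post index procedure". The justification column of Table 3-1 adds the purpose: "Serious adverse events are being collected at 30 days in order to detect any event with a late onset".

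The contact that serves this endpoint has a window. Table 7-1 heads the last column "Day 30 visit (± 3 Days) Office/ Telephone" and places the End of Study form in it. Section 7.6 describes the task at both follow-up contacts: "All enrolled subjects will be seen in person or evaluated via telephone to screen for any post-procedure adverse events". Section 7.7 repeats the window: "Subjects will be followed for 30 days (± 3 days) post index procedure".

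Other provisions also bear on capture:

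- Section 16.1 requires that any reportable event after enrolment, "whether during or subsequent to the procedure, must be recorded in the eCRF".
- Table 16-3 sets the duration of the SAE reporting duty: "Reporting required through the end of the study". The same table shows that the AE form holds the date of the event.
- Section 14 gives the sponsor's personnel direct access to source documents. Section 18.1 has monitors review those documents in support of the safety review.

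Sections 8.1 and 8.3.3 set no hypothesis and plan frequency summaries only.

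**The concern.** The endpoint promises 30 days, yet a site may close a subject's follow-up on day 27 and still comply. The early contact would not be logged as a deviation, and Table 7-1 schedules no later contact. The days left out are the last ones, which are the days that the stated purpose of catching late-onset events depends on.

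If SAEs are counted by onset date up to day 30, an early contact can lose events but never add them, so the reported frequency would be too low. The report would then give a 30-day SAE frequency for a group in which some subjects were actively screened only to day 27, 28 or 29. For a safety endpoint, an error toward a better-looking result deserves a check of its size.

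**Working it through.** The plan states no expected SAE rate, precision or power, so there is no figure of its own to reproduce.

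**Inputs from the documents.** Horizon 30 days (Table 3-1); final contact on days 27 to 33 (Table 7-1); up to 1000 subjects (Synopsis, Section 4).

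**Assumptions.** True 30-day related-SAE risk of 3%, 6% or 10%. Onset at constant hazard, or exponential with a mean of 15 or 5 days, truncated at day 30. Contact days uniform over 27 to 33. Nothing learned after the contact, which makes every loss below an upper bound.

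**Unscreened days.** The gap is max(0, 30 − d) for contact day d: 3, 2, 1, 0, 0, 0, 0. Three of the seven days (3/7 = 43%) fall before day 30. The mean gap is (3 + 2 + 1)/7 = 6/7 = 0.86 day, or 0.86/30 = 2.86% of the period. The maximum is 3/30 = 10%.

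**Share of 30-day events missed.** For d < 30 this is 1 − F(d)/F(30), where F is the cumulative onset distribution. The uniform column averages over the seven days.

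| Onset pattern | Contact on day 27 | Contacts uniform, days 27–33 |
|---|---|---|
| Constant hazard | 10.0% | 2.86% |
| Exponential, mean 15 days | 3.5% | 0.97% |
| Exponential, mean 5 days | 0.20% | 0.055% |

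**Events missed per 1000** = share × risk × 1000, with contacts uniform:

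| Risk | Constant | Mean 15 | Mean 5 | 95% half-width, events per 1000 |
|---|---|---|---|---|
| 3% | 0.9 | 0.3 | 0.02 | 11 |
| 6% | 1.7 | 0.6 | 0.03 | 15 |
| 10% | 2.9 | 1.0 | 0.06 | 19 |

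The half-width is 1.96 × √(p(1 − p)/1000); at 6% it is 1.96 × √(0.06 × 0.94/1000) = 1.47 points. In the constant-hazard case at 6%, the reported frequency would be 6% × (1 − 0.0286) = 5.83%. If every contact fell on day 27, the losses at 6% would be 6.0, 2.1 and 0.12 events. At 10% with constant hazard the loss would be 10 events, still inside 19.

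**Direction.** The loss is downward only if events are cut at day 30 by onset date. The lead-in to the secondary endpoints in Table 3-1 says they are recorded through follow-up, and Section 7.7 defines follow-up with the window. If the endpoint is read as what the final contact finds, events on days 31 to 33 also count. The mean excess is then (1 + 2 + 3)/7 = 6/7 day, equal to the mean gap. Under uniform contacts and constant hazard, mean observation is exactly 30 days and the net bias is about zero.

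**What moving the window could cost.** Suppose the window were moved to open on day 30. A subject who then misses the final contact was last screened at about day 3 and loses 1 − F(3)/F(30) of the events: 90.0%, 79.0% or 54.8% for the three onset patterns. The gain is cancelled when extra missed contacts reach 2.857/90.0 = 3.2%, 0.968/79.0 = 1.2% or 0.055/54.8 = 0.1% of subjects.

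**The case for a change.** The strongest case for acting is that the mismatch lies in the text and nothing scheduled closes it. Section 6.4 defines the end of study partly as completion of the last visit. If Table 16-3 is read per subject, the duty to report SAEs could itself end on day 27, and the upper bounds above become the estimates. Being smaller than sampling error does not make a bias disappear. The analysis section also gives no onset-date rule and does not ask how many subjects were followed to day 30.

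Much of this stands. Sections 6.4 and 7.7 are worded differently, and the counting rule is unstated. The argument does not reach a change in the plan, for three reasons:

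- Capture after an early contact is not limited to what sites volunteer. Monitors review source documents under Section 18.1, and SAEs such as deaths and hospital admissions tend to leave records. This does not guarantee a check of days 28 to 30 for every subject, but it makes total loss unlikely.
- The missing counting rule can be applied at analysis from data already collected, because the event date is on the form.
- A moved window is a trade. Under Section 13.3 it needs ethics approval before use, at up to 40 sites, and nothing in the documents shows that later contacts would be completed as often.

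**Conclusion.** No change to the plan follows. The plan allows up to 3 of the 30 days to pass without a scheduled screen, and if events are counted by onset date this can slightly understate the related-SAE frequency. Under the assumptions tried, the loss with evenly spread contacts is between 0.02 and 2.9 events per 1000. Even with every contact on day 27, constant hazard and 10% risk, it is 10 per 1000 against a half-width of 19. These figures rest on assumed risks, onset patterns and contact days, and on nothing being learned after the contact, so the documents alone cannot fix the true size.

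The endpoint is descriptive, no hypothesis or threshold depends on it, and the primary endpoint is untouched. A window around a 30-day contact is a fair trade between exact timing and completeness. The remaining gap is one that analysts fill sensibly: count by recorded onset date through day 30, and report how many subjects had their final contact on or after day 30. The difference between Sections 6.4 and 7.7 is loose wording, which can be tidied if the protocol is amended for another reason.
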